2.3 Control Algorithm

The myCordella PMP will be able to calculate simple trends in the mean PA pressure (mPAP) of a patient and identify the time-points when treatment needs to be adjusted for each patient based on a defined ruleset (Appendix 14.5 Guidelines for managing HF using Pulmonary Artery Pressures). The goal for all the patients (HFrEF and HFpEF) is to adjust and maintain their mPAP within the normal range of 10-25 mmHg, adjusted for the seating position, which will be achieved at increments of 10mmHg until desired mPAP goal has been reached. After each patient receives the sensor their baseline pressure will be defined a few days after the implant procedure based on the initial home readings. The myCordella PMP will notify the physician to modify treatment based on the 7-day moving average trends and thresholds defined in the Guidelines in Appendix 14.5.

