8.1.16 Cordella PA Sensor Implant Procedure

At the Cordella PA Sensor Implant Visit, the Sensor, which is pre-mounted on a catheter Delivery System, will be delivered according to the system's IFU. Once deployed, the Sensor PAP will be calibrated using the systems fluid-filled catheter as part of an RHC. The calibration coefficients for that Sensor/subject will be recorded in the CalEQ and stored in the CDAP, allowing for consistent PAP calculations throughout the life of the Sensor.

Subjects will be observed until stable (per clinicians' discretion) and discharged home with post-RHC instructions and instructions to take their PAP measurements daily, which will be wirelessly transmitted to a secure website. Additional PAP measurements (seated and supine) will be performed within 24 hours of discharge. The study site should also instruct subjects to return for a catheter insertion site check per their standard-of-care. Before discharge, seated Cordella PA Sensor PAP will be measured via CalEQ.

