8.3.2 Study Visit 2 (Cordella PA Sensor Implant Visit: Admission & Implant)

Before the subjects return for the Cordella PA Sensor Implant Visit, they will be instructed by the Investigator to discontinue use of anticoagulation therapy 1-2 days prior to the procedure. The investigator should consider utilizing another anticoagulant per the site's standard-of-care as bridge therapy to Cordella PA Sensor placement in subjects who were on anticoagulation therapy.

Implant procedures for the Cordella PA Sensor are described in detail in section 6 of the IFU, which will be provided to each site at study start.

Implants may be performed via RHC using percutaneous venous access.

In case the Cordella PA Sensor Implant is attempted but not completed, subjects will be followed through 30 days for safety purposes.

It is critical that accountability of the device is maintained for research records. Federal regulations require that the lots / ID number of the device are appropriately noted and tracked (please also see Section 2.4).

The following study procedures will be performed during this visit:

- Cordella PA Sensor implant
- RHC PAP: diastolic, systolic, mean, HR, RAP, Pulmonary Capillary Wedge Pressure (PCWP), CO, Cardiac Index (CI), RVP: diastolic, systolic, end diastolic
- Cordella PA Sensor PAP: diastolic, systolic, mean, pulse (via CalEQ):
 - after calibration
 - seated and supine before discharge or at home (within 24 hours)
- Set Up/Subject Training: Cordella™ HF System (myCordella™ Tablet & Peripherals)
- Subject Training/Subject Use: CorPASS (myCordella™ Patient Reader and Dock)
- Abbreviated Physical Examination
- Concurrent/Cardiac Medications
- Adverse Event

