3.3. Secondary Efficacy Endpoints

1. Incidence of HF Hospitalizations or all-cause mortality at 12 months
2. Number of HF Hospitalizations at 6 and 12 months post-implant compared to the number of HF Hospitalizations in the 6 and 12 months prior to implant
3. Comparison of the number of HF Hospitalizations or Emergency Department/ Hospital Outpatient IV diuretic visits of Cohort #1 and Cohort #2 + #3 at 6 and 12 months post implant
4. Change of N-terminal pro B-type Natriuretic Peptide (NT-proBNP) from Baseline through 6 and 12 months
5. Combined outcome of:
 - a. First and recurrent HF Hospitalizations
 - b. Heart failure Emergency Department/ Hospital Outpatient IV diuretic visits
 - c. all-cause mortalityat 6 months, added together with equal weighting into a total number of events.
6. Heart failure hospitalization or HF Emergency Department/ Hospital Outpatient IV diuretic visits at 6 and 12 month
7. Cardiac and all-cause mortality
8. Days Alive and Out of Hospital (DAOH)
9. Intravenous (IV) diuretic visits
10. Heart failure related Medication changes
11. Change in PAP:
 - a. From Baseline through 6 and 12 months in subjects with a baseline mPAP
 - i. above target range
 - ii. within or below target range
 - iii. Overall
 - b. Before and after 6-Minute Walk Test
12. Percentage of device success as documented by ability of the System to successfully transmit PAP data
13. Subject Outcome Measures, measured by Kansas City Cardiomyopathy Questionnaire (KCCQ)
14. Functional status improvement, as measured by NYHA and 6-Minute Walk Test
15. Health Economic Analysis (will be covered separately)

This document is confidential.

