5.2. Key Definitions

Age

Age at screening is derived in the database and this value will be used for all analyses.

Definition of Baseline for safety assessments

Baseline will be defined as the last available value prior to the implant of Cordella PA Sensor and may be at any visit between Screening (V1) and Cordella PA Sensor Implant Visit (V2).

Definition of Baseline for PAP measurements

Baseline will be defined as value at Implant Visit (V2) obtained before discharge .

Change from Baseline

Absolute change from baseline:

Absolute change = Post-baseline value –baseline value

Time to Onset of AE

Time to onset of AE [days] = Date of start of AE – Date of implant of Cordella PA Sensor + 1

Start Day of concomitant medication

If medication starts before date of implant of Cordella PA Sensor:

Start Day of Medication = Date of start of medication – Date of implant of Cordella PA Sensor

If medication starts at/after date of implant of Cordella PA Sensor

Start Day of Medication = Date of start of medication – Date of implant of Cordella PA Sensor + 1

Incomplete start dates of medication will not be imputed. Start day of medication will be missing.

Stop Day of concomitant medication

If medication stopped before date of implant of Cordella PA Sensor:

Stop Day of Medication = Date of end of medication – Date of implant of Cordella PA Sensor

If medication stops at/after date of implant of Cordella PA Sensor

This document is confidential.

Stop Day of Medication = Date of end of medication – Date of implant of Cordella PA Sensor + 1
Incomplete end dates of medication will not be imputed. Stop day of medication will be missing.

Definition of study completed/discontinued/ongoing

A subject will be defined as study ‘completed’/‘discontinued’ based on the eCRF information. At the time of the pre-defined main analysis, subjects which are ongoing at date of cut-off will be counted as ‘ongoing’.

Time since first diagnosis of heart failure

Time since diagnosis [months] = ((Date of Screening – Date of first HF diagnosis)+1)/30

Exposure time:

which would be exact 6 or 12 months (180 or 365 days respective) post-implant visit for subjects who are still in the study at/after this timepoint.

which would be [date of last available date – date of Implant visit + 1] for subjects who withdraw from study prior to month 6 or 12 (180 or 365 days respective) post-implant visit.

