7.1.14. Change in PA pressure

Change from baseline in PAP parameters collected via CorPASS: pulmonary artery pressure systolic, pulmonary artery pressure diastolic, pulmonary artery pressure mean and pulse will be presented by treatment group by means of descriptive statistics at before and after 6-minute walk test.

mPAP will be summarized by 'Above target range', 'Within or below target range', and 'Overall' for subjects with a baseline mPAP, at all study visits as described in [Appendix 1: Time and Event Schedule](#) including post implant measurement, and sitting vs. supine measurements. Shifts in mPAP from baseline over all post-baseline visits will be presented. Target range of mPAP is 5-20 mmHg. When there are more than one available results collected on same visit, please use the earliest one.

Analysis will be done based on mITT population, and PP population. Prior to the date of cut-off for the main analysis, it will be confirmed, if analysis based on PP population will be required.

This document is confidential.

7.1.15. Percentage of device success as documented by ability of the System to successfully transmit PAP data

For the analysis of this endpoint, external data, provided by Endotronix, will be used. The provided data will include information if the missing PAP data are due to the System issues.

Following derived parameters will be presented:

- A) Total overall number of days of data collection, defined as the sum of all planned collection days (until end of study for final analysis or date of early discontinuation or date of cut-off or date of V6, Month 12 for the main analysis, whichever is smaller) of all subjects, excluding the days with missing data collection due to the subject's missing data transmission.
- B) Number of days with missing overall successful transmission of the collected data due to the System issues, defined as the sum of all unavailable days due to the System issues (until end of study for final analysis or date of early discontinuation or date of cut-off or date of V6, Month 12 date for the main analysis, whichever is smaller) of all subjects
- Overall device success rate of transmission (%), defined as $A-B/A * 100$
- Per subject device success rate will be calculated similar to the rules above, based on per subject data only.

Per subject device success rate will be presented by means of descriptive statistics, overall device success rate as percentage, other parameters will be presented using counts.

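### One pre-discharge PAP reading both sets the endpoint 11a stratum and serves as the baseline for change, which adds regression to the mean to the two target-range groups

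*SAP*

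**What the plan says.** SAP 5.2 gives PAP its own baseline rule: "Baseline will be defined as value at Implant Visit (V2) obtained before discharge". It names no posture and does not say which implant-visit reading is meant. SAP 7.1.14 adds a rule for multiple results: "When there are more than one available results collected on same visit, please use the earliest one".

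Endpoint 11a in SAP 3.3 is PAP change "From Baseline through 6 and 12 months in subjects with a baseline mPAP" above target, within or below target, and overall. SAP 7.1.14 carries this out descriptively: "mPAP will be summarized by 'Above target range', 'Within or below target range', and 'Overall' for subjects with a baseline mPAP". It adds shift tables and a target range of 5-20 mmHg. Its analysis sets are mITT and PP only; Cohort #1 is not included.

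The protocol describes the implant-visit readings in two places. Section 8.3.2 lists a sensor reading after calibration and then readings "seated and supine before discharge or at home (within 24 hours". Section 8.1.16 says "Before discharge, seated Cordella PA Sensor PAP will be measured via CalEQ" and also "Additional PAP measurements (seated and supine) will be performed within 24 hours of discharge". Separately, protocol 2.3 says of implanted patients that "their baseline pressure will be defined a few days after the implant procedure based on the initial home readings", and gives a target range of 10-25 mmHg adjusted for seating position.

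**The concern.** When the same reading classifies a subject and is then subtracted to give change, its error enters both steps. Subjects land above 20 mmHg partly because that reading happened to be high, and their later readings tend to come back down. Below the cut the reverse happens. The trial is single-arm and Cohort #1 is left out of this analysis, so nothing in the plan separates this drift from an effect of PAP-guided care. A fall in the above-target group is the result a reader would take as evidence that the system works.

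The choice of reading is also open. The post-calibration, seated and supine readings can all precede discharge. The earliest-result rule, taken literally, could select the post-calibration reading made during the procedure. A supine reading taken at home within 24 hours cannot be a baseline at all. Two programmers could follow the text and derive different baselines.

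**Working it through.** The documents give no variance, power or expected change for this endpoint, so there is no stated figure to reproduce. The check estimates how large the artefact could be when there is no true change.

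**Inputs**
- Cut-off c = 20 mmHg (SAP 7.1.14).
- Mean and SD of mPAP: 22.5 and 11.8 (sensor), 25.2 and 8.5 (catheter), from the 15-patient first-in-human study in protocol 3.3. These are treated as the total SD, S, of one reading.
- Within-subject SD, w: 3 or 5 mmHg. **Assumed.**
- k = number of readings averaged for baseline, with independent errors (assumed).

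**Formulas** (normal readings, no true change)
- sd_k² = S² − w² + w²/k
- rho_k = (S² − w²)/sd_k²
- a = (c − mean)/sd_k
- Above target: −(1 − rho_k) · sd_k · phi(a)/(1 − Phi(a))
- Within or below: +(1 − rho_k) · sd_k · phi(a)/Phi(a)

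**Worked case:** mean 22.5, S = 11.8, w = 5, k = 1.
- rho = (139.24 − 25)/139.24 = 0.820
- a = (20 − 22.5)/11.8 = −0.212; phi(a) = 0.390; Phi(a) = 0.416
- Above: −0.180 × 11.8 × 0.390/0.584 = −1.4 mmHg
- Within or below: +0.180 × 11.8 × 0.390/0.416 = +2.0 mmHg
- Overall: the weighted sum, 0.584 × (−1.4) + 0.416 × 2.0, is about 0.

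**All cases** (spurious change in mmHg, above / within or below)

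| Mean, SD | w | One reading | Mean of 7 |
|---|---|---|---|
| 22.5, 11.8 | 3 | −0.5 / +0.7 | −0.1 / +0.1 |
| 22.5, 11.8 | 5 | −1.4 / +2.0 | −0.2 / +0.3 |
| 25.2, 8.5 | 3 | −0.5 / +1.3 | −0.1 / +0.2 |
| 25.2, 8.5 | 5 | −1.3 / +3.6 | −0.2 / +0.7 |

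**Sensitivity**
- If the first-in-human SDs are read as true between-subject SD rather than total SD, the upper ends fall to 1.3 and 2.9 mmHg.
- If single-reading reliability is instead assumed to be 0.6 to 0.9, the ranges are 0.4-3.2 mmHg (above) and 1.0-4.4 mmHg (within or below). With seven readings they are 0.1-0.5 and 0.2-0.8 mmHg.
- With a cut at 25 mmHg, the upper limit in protocol 2.3, and w of 3 to 5, one reading gives 0.7-2.3 and 0.5-2.4 mmHg.
- A simulation of 2,000,000 subjects (mean 22.5, SD 11.8, reliability 0.8, cut 20) gave −1.58, +2.21 and −0.01 mmHg for above, within or below, and overall. The formula gives −1.58 and +2.21 for the two strata.

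**The case against.** The strongest reply is that the SAP baseline matches a reading the protocol requires. Section 8.1.16 calls for a seated CalEQ reading before discharge in implanted subjects and describes those around discharge as additional. A reader might infer that the SAP rule leaves many subjects with no baseline. The documents do not support that: seated baselines are largely preserved, and the loss falls mainly on supine readings taken at home. The looser wording of 8.3.2 is partly a tension within the protocol itself.

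A reader might also infer that the SAP contradicts a protocol-defined analysis baseline. Protocol 2.3 describes the algorithm that prompts clinicians. It supports averaging home readings but does not fix the baseline for endpoint 11, and the endpoint sections define none.

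Other parts of the reply stand too. The protocol itself prescribes the strata, and it prescribes the overall group, where the artefact is about zero. The tables indexed for mPAP against baseline are shifts in category, so the mmHg figures do not map onto a listed table, although the same mechanism moves subjects across the cut. The size rests on assumed variability and a small external sample. Home readings from the first week come after implant, when guided treatment has begun.

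None of this removes the mechanism. The same reading is still classifier and baseline, with no control and no adjustment.

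**Conclusion.** The point holds as a minor one. The direction is certain whenever readings vary within a subject: a spurious fall above target and a spurious rise within or below it. The size, about 0.5-1.4 and 0.7-3.6 mmHg, depends on a within-subject SD of 3-5 mmHg and on borrowing the first-in-human spread, so it should be read as an illustration. The cause is using one reading for two roles, not the exclusion of home readings as such; a single home reading would do the same.

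A reader might go further and doubt the trial's efficacy conclusion. That does not follow. Endpoint 11 is descriptive, lies outside the tested sequence of the primary and first secondary endpoints, and its overall group is essentially unbiased. That the baseline is one reading is inferred from the singular wording of SAP 5.2 and the earliest-result rule; the SAP does not say so outright.

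**What to change.** - **SAP 5.2:** accept implant-visit readings taken before discharge or at home within 24 hours, as protocol 8.3.2 allows. Exclude the post-calibration reading. State posture and source, and match posture between baseline and follow-up.
- **Endpoint 11a (SAP 7.1.14):** assign the stratum and compute seated change from the mean of the initial seated home readings, for example the first 7 days, with a stated minimum number. This is consistent with protocol 2.3. Report the single implant-visit analysis alongside.
- **Stratum cut-off:** SAP 7.1.14 (5-20 mmHg) and protocol 2.3 (10-25 mmHg, adjusted for seating) differ and must be reconciled, because the cut-off defines the groups.
- **SAP section 10:** record the baseline choice, which is not listed there now.

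The cost is SAP wording and programming, since home readings are already transmitted daily. The downside is that treatment changes in the first week may slightly lower the baseline. That is conservative for a claimed fall, and the single-reading analysis alongside lets a reader see the difference.

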5.3. Missing Data

It is anticipated that there will be little or no missing data that would impact the ability to assess the primary endpoint. The primary efficacy analysis will be based on the mITT population and the primary safety analyses will be based on the population of subjects who underwent a device implant. The primary analysis methods naturally handle missing data by censoring subjects who have dropped out. For the primary safety analyses, the endpoints can be considered as dichotomous and the extreme cases as well as a tipping point analysis can be presented.

For all other analysis, missing data will not be replaced.

5.4. Visit Windows

Every attempt should be made to perform evaluations at the designated time points. However, for visits conducted at Month 1 and 3 there is a window of +/-7 days, for visits at Month 6 there is a window of +/-14 days and after Month 6 (Month 12, 18, 24 and Year 3) there is a window of +/-30 days. All visits will be summarized according to the nominal visit.

5.5. Pooling of Sites

Subjects will be pooled across sites for analysis of study endpoints. Sites with at least 20 subjects will retain their identities. Smaller sites will be ranked in decreasing order of size (site identification numbers, smallest first, will be used to break ties) and cumulatively pooled until pooled sites of no less than 10 subjects are achieved. After this pooling process, it will be tested for homogeneity in the treatment effects across site by using the same poisson model for primary endpoint but to add pooled site as a covariate. The homogeneity test will be conducted at the 0.15 level effect for pooled_site.

```
proc genmod data = xxx;  
    class pooled_site;  
    model number of events = pooled_site / type3 dist=poisson  
        offset=log(exposure_time);  
run;
```

In case homogeneity in the rate across sites is not given, an explorative analysis will be performed as post-hoc analysis, to evaluate in a first step what are the differences between the sites which may lead to different rates across sites. The possible factors will be evaluated during this exploratory analysis. In a second step a more complex analysis, e.g. Bayesian hierarchical model of HF event rates across pooled sites which is

This document is confidential.

essentially treating site as a random effect could be performed. The final decision on the analysis to be performed will be evaluated outside of this SAP. Pooling of sites will be based on the mITT and PP populations.

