6.2 Number of Clinical Sites and Subjects

The trial will be conducted at up to hundred-twenty (120) sites in the US and Europe. Screening will continue until a maximum of 535 subjects are successfully implanted (all Cohorts).

Of these 535 subjects, up to 85 subjects (cross- over from former **Control Arm**) will continued to be followed in Cohort #1.

At least 50% of the total subjects will be enrolled in the US. No single clinical site will be allowed to enroll more of 20% of the total subjects into the study. In addition, clinical sites are not allowed to implant more than thirty (30) subjects into the study without prior written approval from Endotronix.

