10.6 Analysis sites

The study will be conducted such that: 1) the same protocol will be used at each study site; 2) site investigators and personnel will receive uniform training; and 3) central data management, and

monitoring will be applied with equal rigor at all sites. The diversity of hospital and clinical practice settings will add to the scientific validity and generalizability of the findings.

Subjects will be pooled across sites for analysis of study endpoints.

Sites with at least 20 subjects will retain their identities. Smaller sites will be ranked in decreasing order of size (site identification numbers, smallest first, will be used to break ties) and cumulatively pooled until pooled sites of no less than 10 subjects are achieved. After this pooling process, we will test for homogeneity in the treatment effects across site with a likelihood ratio test of the hypothesis that all sites have the same rate. The homogeneity test will be conducted at the 0.15 level based on Fisher's exact test.

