2.2. Brief Description

This is a prospective, open-label, single arm, multi-center clinical trial evaluating the safety and efficacy of the Cordella™ Pulmonary Artery Sensor System in New York Heart Association (NYHA) Class III heart failure (HF) subjects compared to a Performance Goal (PG).

All eligible subjects get implanted the Cordella PA Sensor. As part of the Cordella PA Sensor System (CorPASS), it intends to measure, record, and transmit pulmonary artery pressure (PAP) data from NYHA Class III heart failure patients at home to clinicians for assessment and patient-centered HF management, with the goal of reducing heart failure hospitalizations.

The study is planned to be conducted in up to 120 sites in the United States and Europe. The study population includes male and female subjects, ≥ 18 years of age with a diagnosis of NYHA Class III heart failure.

With this amendment to the protocol/CIP, subjects will be categorized into three (3) different cohorts:

1. Cohort #1- Previously enrolled Control Arm subjects
 - Subjects in this cohort will be unblinded to their PAP measurements and informed about their previous group assignment and continue their Follow-up visit schedule
 - Additionally, subjects will be asked, throughout the remaining Follow-up period, to complete a regular subject survey on their experience with PAP Measurements and PAP Values.
 - Clinicians will be unblinded to their PAP measurements and start managing the patients to target PA pressures per protocol/ CIP and according to Guideline Directed Medical Therapy (GDMT)
 - Additionally, the clinical site will be asked to contact the subject on a regular basis to discuss their PAP values
 - Separate analysis (safety and effectiveness) will be performed for Cohort #1
2. Cohort #2- Previously enrolled Treatment Arm subjects
 - As of month 12 subjects in this cohort will be able to see their own PAP measurements for the remaining duration of the study.
 - Clinicians will continue to manage the patients to target PA pressures per protocol/CIP and according to GDMT
 - All primary and secondary safety and effectiveness analyses will be performed
3. Cohort #3- Newly enrolled subjects

This document is confidential.

- Subjects will participate in the Screening/ Enrollment Visit, Cordella PA Sensor Implant Visit, and Follow-Up Visits.
- Clinicians will manage the patients to target PA pressures per protocol/ CIP and according to GDMT.

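### The site-homogeneity test in SAP 5.5 does not hold its 0.15 level: about 0.18 to 0.27 with no within-subject clustering, and more with it

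*SAP*

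**What the plan says.** SAP 5.5 first forms the pools. "Sites with at least 20 subjects will retain their identities"; smaller sites are ranked by size and "cumulatively pooled until pooled sites of no less than 10 subjects are achieved". It then fits "model number of events = pooled_site / type3 dist=poisson" with log exposure as the offset and no scale or dispersion option, and "The homogeneity test will be conducted at the 0.15 level effect for pooled_site". If homogeneity fails, the SAP calls for an exploratory post-hoc look at what differs between sites. A more complex model may follow, for example a Bayesian hierarchical one across pooled sites, with the final choice made outside the SAP.

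Protocol 10.6 describes the same check in two ways. One sentence plans to test "with a likelihood ratio test of the hypothesis that all sites have the same rate". The next says "The homogeneity test will be conducted at the 0.15 level based on Fisher's exact test".

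The number of pools depends on recruitment. "The study is planned to be conducted in up to 120 sites in the United States and Europe", and "clinical sites are not allowed to implant more than thirty (30) subjects into the study without prior written approval" from the sponsor. For the primary endpoint, SAP 7.1.2 adds a negative binomial sensitivity analysis because events may be correlated within a subject. SAP 5.5 has no counterpart for the site test.

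**The concern.** The test treats each pool's event count as Poisson, with variance equal to its mean, and refers the likelihood-ratio statistic to a chi-square distribution. Both steps are doubtful here.

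- **Sparse counts.** The chi-square approximation to the likelihood-ratio statistic is poor when many pools expect only a handful of events.
- **Clustered counts.** The endpoint counts all heart failure hospitalizations plus death. A few subjects with repeated admissions raise the variance of their pool's count, and an unscaled Poisson test reads that as a difference between sites.

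A screening test at 0.15 is meant to flag about one in seven trials with identical sites. If it flags many more, a positive result says little about sites, yet it opens unspecified modelling of the primary event rate in a single-arm trial intended for a premarket submission. A reader could not tell a false alarm from a real site difference.

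**Working it through.** **Inputs from the documents.** 450 implanted and 406 evaluable subjects; assumed 6-month rate 0.34; performance goal 0.43; one-sided alpha 0.025 (SAP 2.4.1). Pooling rule and level 0.15 (SAP 5.5). Up to 120 sites (SAP 2.2). About 10% dropout by 6 months (Protocol 6.1).

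**Assumed, because the documents are silent.** Site sizes, hence the number of pools; the dispersion; and a split of the 0.34 into 0.28 hospitalizations and 0.06 deaths per subject where deaths are modelled.

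**The plan's own power figure.** Expected events are 406 × 0.43 = 174.6 under the null and 406 × 0.34 = 138.0 under the alternative. The exact Poisson test rejects at 148 events or fewer, with alpha 0.022 and power 0.814. The stated power above 80% reproduces, so the rate is being read as intended.

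**Pool sizes.** At most 450/10 = 45 pools. If 21 sites reached 20 subjects and one reached 30, there would be 21 × 20 + 30 = 450 subjects in 22 pools. With all 120 sites open the mean is 450/120 = 3.75 subjects per site, which points towards the upper end. Expected events per pool are 10 × 0.34 = 3.4, 15 × 0.34 = 5.1 and 20 × 0.34 = 6.8.

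**Test.** With Y_g the events in pool g and μ_g the pool's exposure times the overall rate, the statistic is 2 Σ Y_g log(Y_g/μ_g), referred to chi-square on G − 1 degrees of freedom at 0.15. I read the SAP's type 3 request as the likelihood-ratio test that the protocol names.

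**Simulated level with identical sites, full follow-up, 40,000 trials per cell.** Subjects have gamma frailty with variance k, so the per-subject variance/mean ratio is 1 + 0.34k.

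| Pools | k=0 (1.00) | k=0.5 (1.17) | k=0.75 (1.255) | k=1 (1.34) | k=2 (1.68) |
|---|---|---|---|---|---|
| 22 | 0.179 | 0.343 | 0.430 | 0.509 | 0.757 |
| 30 | 0.201 | 0.405 | 0.506 | 0.594 | 0.848 |
| 37 | 0.229 | 0.459 | 0.569 | 0.668 | 0.900 |
| 45 | 0.262 | 0.527 | 0.647 | 0.739 | 0.940 |

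The rate passes one half at a ratio of about 1.17 with 45 pools and 1.34 with 22.

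**With deaths, 10% dropout and truncated exposure,** the range from 22 to 45 pools is 0.18–0.27 at k = 0, 0.29–0.45 at k = 0.5, 0.40–0.61 at k = 1 and 0.60–0.83 at k = 2. With 22 pools one half is reached only at k = 1.5 (0.503).

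**Separating the two causes.** An unscaled Pearson chi-square holds 0.15–0.16 at k = 0, so the excess there comes from the likelihood-ratio approximation. At k = 1 it rises to 0.37–0.48 in the model with deaths and dropout, so the rest is clustering.

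**Candidate repairs, nominal 0.15.**

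| Test | Simulated level |
|---|---|
| Pearson chi-square ÷ dispersion from the model without site | 0.12–0.16 |
| Permuting subjects across pools (1,000 trials, simulation error about 0.011) | 0.14–0.17 |
| Negative binomial likelihood ratio | 0.17–0.23 at k = 0; 0.24–0.46 at k = 1 to 4 |
| Scale taken from the model that contains pooled_site (25–38 pools) | 0.19–0.54 |

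**The case against.** The strongest reply is that little depends on this test. SAP 5.5 opens by pooling subjects across sites without condition. SAP 7.1.1 fixes success by the upper bound against 0.43 and the observed rate against 0.37, with no mention of site. The SAP's table index lists the test as supportive, and 0.15 is already a lenient screening level. All of that stands. A reader might infer that a false alarm endangers the primary conclusion; the documents do not support that, because what follows a rejection is already labelled exploratory and post hoc.

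A reader might also infer that the test would report site differences in most trials that have none. That needs a dispersion figure, and neither document gives one. With no clustering the rate is 0.18 to 0.27, and once deaths and dropout are modelled even k = 1 gives more than one half only with the larger numbers of pools.

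Pool sizes are assumed too: sites of 20 or more stay separate, and fewer, larger pools soften the problem. It is still present at 22 pools (0.18). Finally, if the protocol's Fisher wording governed, these calculations would not apply. But the SAP's code is a Poisson model, and Fisher's test has no place for repeated counts or an exposure offset.

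**Conclusion.** The stated level of 0.15 is not held. Without any clustering the true level is about 0.18 to 0.27, which requires no dispersion assumption, only a number of pools between 22 and 45. Within-subject clustering, which the SAP plans for elsewhere, raises it. Under full follow-up it exceeds one half from a variance/mean ratio of about 1.2 to 1.35; that ratio is plausible for recurrent hospitalizations but is an assumption here. The consequence is bounded: unneeded post-hoc site modelling of unspecified form, and an avoidable question about poolability, with no effect on the primary test. Separately, the two descriptions in Protocol 10.6 are incompatible and must be reconciled. The point is worth correcting because the correction is cheap.

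**What to change.** In SAP 5.5, keep the pools and the 0.15 level but replace the test by one of the following.

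1. **Scaled Pearson chi-square.** Compute Σ (Y_g − μ_g)²/μ_g over pools, divide it by a dispersion estimated from the model without pooled_site, and refer it to chi-square on G − 1 degrees of freedom. Define the dispersion as the subject-level sum of (y − μ)² over the sum of μ, with the usual N/(N − 1) factor. Do not average (y − μ)²/μ over subjects, because early deaths dominate that average. A death on day 5 has μ = 0.34 × 5/180 = 0.0094 and contributes (1 − 0.0094)²/0.0094 ≈ 104, so that one subject adds 104/449 ≈ 0.23 to the estimate.
2. **Permutation test.** Reassign subjects across pools, keeping each subject's event count and exposure together, and compare the observed statistic with its permutation distribution.

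Do not rely only on a negative binomial likelihood-ratio test, or on PSCALE if the scale comes from the model containing pooled_site; neither restores the level. In Protocol 10.6, delete the reference to Fisher's exact test and name the test chosen in the SAP. The cost is a few lines of code and two sentences of wording, with no new data.
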